2.1 Study Variables

2.2 Primary Variables

The hierarchical primary efficacy measures are the absence of anterior chamber cells [REDACTED]

[REDACTED] and the absence of pain [REDACTED]

2.3 Secondary Variables

The secondary efficacy measures include:

- Absence of anterior chamber cells [REDACTED]
- Absence of pain [REDACTED]
- Absence of flare [REDACTED]
- Absence of both anterior chamber cells and flare [REDACTED]
and
- Use of rescue medication on or prior to each visit and overall.

2.4 Safety Variables

Safety variables to be summarized will include visual acuity, intraocular pressure (IOP), occurrence of adverse events (AE), and measurements from slit lamp biomicroscopy and dilated indirect ophthalmoscopy.

2.5 Statistical Hypotheses

The hierarchical statistical hypotheses for evaluating the objectives of the study are as follows:

Primary Endpoint:

[REDACTED]

[REDACTED]

[REDACTED]

[REDACTED]

[REDACTED]

Hierarchical Primary Endpoint:

[REDACTED]

[REDACTED]

[REDACTED]

[REDACTED]

[REDACTED]

Multiple comparison adjustments for testing OCS-01 BID and OCS-01 QD versus placebo (vehicle) in the absence of anterior chamber cells will not be made [REDACTED]

[REDACTED] A hierarchical testing strategy will be employed for testing absence of pain; statistical inference will only be made on the absence of pain endpoint if the corresponding OCS-01 dose (BID or QD) demonstrated statistical superiority over placebo (vehicle) in the absence of anterior chamber cells.

3. Study Design and Procedures

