7.1.3 Primary Efficacy Analyses

The hierarchical primary efficacy analyses are as follows:

1. Difference between the two treatment arms in the proportion of study eyes with absence of anterior chamber cells [REDACTED]

If the proportion of study eyes with absence of anterior chamber cells [REDACTED] is statistically significantly higher for OCS-01 versus placebo (vehicle) [REDACTED]
[REDACTED]

2. Difference in the proportion of study eyes with absence of pain [REDACTED]

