This SAP describes the data that will be analyzed and the subject characteristics, efficacy, and safety assessments that will be evaluated. This SAP provides details of the specific statistical methods that will be used. The statistical analysis methods presented in this document will supersede the statistical analysis methods described in the clinical protocol. If additional analyses are required to supplement the planned analyses described in this SAP, they may be completed and will be identified in the clinical study report.

2. Study Objectives

The primary objective of this study is to evaluate the efficacy and safety of OCS-01 once daily (QD) and twice daily (BID) compared to placebo (vehicle) BID in the treatment of inflammation and pain following cataract surgery.

The secondary objective of this study is to evaluate the optimal dosing frequency of OCS-01 (QD versus BID) in the treatment of inflammation and pain following cataract surgery.

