8.5 Adjustments for Multiplicity

The hierarchy of statistical hypotheses for testing is described in Section 2.5.

[REDACTED]

9. Disposition of Subjects

Disposition of subjects will be summarized for the [REDACTED]

[REDACTED]

[REDACTED]

[REDACTED]

[REDACTED]

Disposition of subjects will also be summarized among [REDACTED]

[REDACTED]

[REDACTED]

The number and percentage of subjects with major protocol deviations will be summarized by [REDACTED]

[REDACTED]

[REDACTED]

[REDACTED]

[REDACTED]

[REDACTED]

[REDACTED]

In addition, subject listings will be provided that include informed consent date, inclusion and exclusion criteria violations, and exclusions from the PP population.

Details of the study randomization, including randomization date and time, randomized treatment and actual treatment, will also be included within a subject listing.

10. Demographic and Pretreatment Variables

The demographic variables collected in this study include [REDACTED]

[REDACTED]

[REDACTED]

[REDACTED]

Age (years) will be summarized, overall and by treatment, using [REDACTED]

[REDACTED]

[REDACTED]

[REDACTED]

A subject listing that includes all demographic variables will be provided.

11. Medical History and Concomitant Medications

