13.1 Primary Analysis

The hierarchical primary efficacy measures are the absence of anterior chamber cells [REDACTED]

[REDACTED] and the absence of pain [REDACTED]

The anterior chamber cell count will be recorded as [REDACTED]

[REDACTED] Anterior chamber cell count is assessed for study eye only. Refer to

Table 2 for details.

Table 2. Anterior Chamber Cell Counts and Grade

Ocular pain will be assessed by the patient [REDACTED]

The observed anterior chamber cell count at Visit 6 will be used and categorized for analysis as follows:

- Absence of anterior chamber cells: [REDACTED]
- Presence of anterior chamber cells: [REDACTED]

Within this analysis, missing values for visits after a subject is discontinued for lack of efficacy or values obtained after subject has received rescue medication will be imputed as failures [REDACTED]

[REDACTED] for analysis. For all other missing data, LOCF will be used to impute the missing anterior chamber cell count grade, and the LOCF value will then be categorized for analysis as “cells present” or “cells absent”.

Derivation of the pain score and absence of pain [REDACTED] will follow the same approach for handling of missing data and handling of pain scores obtained following use of rescue medication.

The primary efficacy variables, the absence of anterior chamber cells at [REDACTED] and the absence of pain [REDACTED] will be summarized by [REDACTED]

For each OCS-01 dose (QD and BID) separately, the primary efficacy analyses will [REDACTED]

SAS® code used to generate the [REDACTED]

[REDACTED]

Comparison of OCS-01 QD versus placebo (vehicle) will be conducted in a similar manner, differing only by the treatment arms which are included within the comparison. Testing for each OCS-01 treatment group versus placebo (vehicle) for the absence of pain variable will use similar code.

[REDACTED]
[REDACTED]
[REDACTED]
[REDACTED]
[REDACTED]
[REDACTED]
[REDACTED]

Anterior chamber cell grade in the study eye at Visit 6 (Day 15) will be summarized by [REDACTED]

[figure not shown]
[figure not shown]
[REDACTED]
[REDACTED]

[figure not shown]
[figure not shown]
Ocular pain score at Visit 4 (Day 4) will be summarized by [REDACTED]

The primary efficacy analysis will be conducted using the FAS.

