13.1.1 SENSITIVITY ANALYSES OF THE PRIMARY EFFICACY MEASURES

To check the robustness of primary efficacy analysis results, the previously described analyses of the primary efficacy measures will be repeated based on alternate handlings of missing data and major protocol deviations.

A series of horizontal black bars of varying lengths, with the longest bar at the bottom containing a small white square.

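### Should the two unadjusted regimen-versus-vehicle tests on anterior chamber cells carry a study-wise error caveat?

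*SAP*

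**What the plan says.** SAP 2.5 (Statistical Hypotheses) sets out the testing scheme. For the first primary measure, absence of anterior chamber cells: "Multiple comparison adjustments for testing OCS-01 BID and OCS-01 QD versus placebo (vehicle) in the absence of anterior chamber cells will not be made". The public text is blacked out directly after these words. For the second, absence of pain, the SAP uses a gate within each dose: "statistical inference will only be made on the absence of pain endpoint if the corresponding OCS-01 dose (BID or QD) demonstrated statistical superiority" over vehicle on cells.

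SAP 8.5 (Adjustments for Multiplicity) has one readable line, "The hierarchy of statistical hypotheses for testing is described in Section 2.5", and is then blacked out. SAP 13.1 treats the regimens one at a time: "For each OCS-01 dose (QD and BID) separately, the primary efficacy analyses will", where the sentence is cut. It adds that the QD comparison differs from the other only in the arms included.

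Protocol 7.1.3 gives the condition for moving from cells to pain as the proportion that "is statistically significantly higher for OCS-01 versus placebo (vehicle"), with blacked-out text on both sides. SAP 13.1.1 says the primary analyses "will be repeated based on alternate handlings of missing data and major protocol deviations". The protocol synopsis gives the phase as 2 and the size as about 150 randomized subjects. No interim analysis is planned.

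**The concern.** Two active regimens share one vehicle arm, and each is tested at the full level. Nothing readable orders the regimens, splits alpha or requires both to win. If the drug did nothing, the trial would have two chances of a false positive on its first primary measure.

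The readable words of protocol 7.1.3 name OCS-01 without a regimen, so a win on either one might be presented as the product's result. Choosing between QD and BID is also the secondary objective, so a significant result for one regimen only could be taken as evidence that the regimens differ. The sensitivity analyses in SAP 13.1.1 deal with missing data and deviations and do not touch multiplicity. At stake is whether a reader of a split result would know that its error control is per test.

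**Working it through.** **Inputs.** From the documents: two tests on cells, one shared vehicle arm, superiority direction only, about 150 subjects, no interim look. Not readable, so assumed: two-sided 0.05 per test (0.025 in the superiority direction) and 1:1:1 allocation, hence 150 / 3 = 50 per arm. The test method and the design response rates are not readable either. The readable text states no familywise error rate, so there is no plan figure to reproduce.

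**1. Chance of at least one false win.** With a shared control arm and equal allocation the two z statistics correlate at 0.5. Then

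P(at least one) = 1 − P(Z₁ < 1.96, Z₂ < 1.96) = 0.0454.

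P(both) = 2 × 0.025 − 0.0454 = 0.0046, so P(exactly one) = 0.0454 − 0.0046 = 0.0408.

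The 4.5% is therefore the rate for at least one false win. A false win on one regimen only is about 4.1%.

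**2. Dependence on the hidden inputs.**

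| Assumption changed | At least one false win | One test |
|---|---|---|
| Allocation QD:BID:vehicle 2:2:1 (correlation 0.667) | 4.25% | 2.5% |
| Allocation 1:1:2 (correlation 0.333) | 4.73% | 2.5% |
| Two-sided 0.025 per test, 1:1:1 | 2.32% | 1.25% |
| Two-sided 0.10 per test, 1:1:1 | 8.78% | 5% |
| Pearson chi-square, 50 per arm, common response rate 10% to 50% | 4.5% to 5.1% | 2.5% to 2.8% |
| Fisher's exact test, same settings | 1.7% to 3.2% | 0.9% to 1.8% |

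Under Fisher's exact test most of the apparent excess over 2.5% goes. At a common rate of 10% or 15% the chance of any false win (1.7% and 2.2%) is below 2.5%.

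**3. Split results when both regimens work equally well.** Pooled z test, 50 per arm, vehicle rate 25% (illustrative rates):

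| Rate on each regimen | Power per dose | Exactly one significant |
|---|---|---|
| 45% | 56% | 33.5% |
| 53% | 83% | 20.6% |
| 60% | 96% | 6.9% |
| 65% | 99% | 2.1% |

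Both regimens are truly effective here, so no win is false. A split result reflects limited power, and its frequency depends entirely on the assumed effect. This is not a multiplicity error.

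**4. Cost of formal control.** Hochberg on cells, same setting. At 25% v 53%, power per dose falls from 83.5% to 81.0% if both regimens work and to 75.3% if only one does. At 25% v 45%, it falls from 55.9% to 51.2% and to 45.4%. The losses are 2.5, 8.2, 4.7 and 10.5 points.

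**5. What the text claims.** SAP 2.5 says no adjustment is made across doses and ties the pain test to the corresponding dose; SAP 13.1 analyses each dose separately. No readable sentence claims familywise control or turns a single-dose win into a product-level conclusion. The protocol 7.1.3 condition is cut on both sides, so its readable middle cannot show that no regimen is named. SAP 1 (Introduction) says the SAP's methods supersede the protocol's, and the SAP is explicit by dose.

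**The case for a change.** The strongest case for acting is that it would cost almost nothing. One sentence saying that a one-regimen win is not controlled for testing two regimens, and does not by itself show that they differ, would need no patients and lose no power. Fixing it before unmasking would prevent a convenient description of a split result afterwards. The 4.5% reproduces, and nearly all false wins would be of this kind: in simulation with a 25% rate in every arm, exactly one regimen won in 4.03% of trials out of 4.58% with any win, or 88%.

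The arithmetic stands, and so does the advice not to read a split result as a QD-versus-BID comparison. But that is advice on interpretation. No readable passage says the secondary objective will be judged by which regimen reaches significance. A statement that no adjustment is made already tells the reader that error control is per test. The rest of that sentence and nearly all of SAP 8.5 are blacked out, and a reason or caveat would naturally stand there, so its absence cannot be asserted. Adjusted p-values labelled supportive would decide nothing.

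**Conclusion.** The concern does not hold. Leaving two regimen-versus-vehicle tests unadjusted is a legitimate, openly pre-specified choice in a phase 2 trial, and nothing readable contradicts it or promises more. Under two-sided 0.05, 1:1:1 and a test that attains its nominal size, the chance of at least one false superiority result on cells is about 4.5% against 2.5% (4.1% for exactly one). With Fisher's exact test at 50 per arm it is 1.7% to 3.2%. These figures describe a known consequence of the declared choice. They rest on an alpha, allocation and test that the public documents do not show. Formal adjustment would exchange that risk for about 2 to 10 points of power per dose in the scenarios examined, which is the sponsor's decision. No change to the plan follows.

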3.1 General Study Design

This study is a multi-center, randomized, double-masked, placebo (vehicle)-controlled study, designed to evaluate the efficacy and safety of OCS-01 ophthalmic suspension (QD versus BID) compared to placebo in treating inflammation and pain following cataract surgery.

Eligible subjects will be randomized [REDACTED] to receive OCS-01 QD, OCS-01 BID, or placebo BID. Subjects will dose 1 drop in the study eye BID for 14 days, beginning 1 day post-surgery in the operated eye. The study will last 20-52 days, including screening and a follow-up visit at Visit 7 (Day 22 ± 2).

3.2 Schedule of Visits and Assessments

The schedule of visits and assessments is provided in **Table 1**.

Table 1: Scheduled of Visits and Measurements

Visit	Measurement	Comments
Initial Visit	Height, Weight, Blood Pressure	
1 Month Follow-up	Blood Pressure, Heart Rate	
3 Month Follow-up	Blood Pressure, Heart Rate	
6 Month Follow-up	Blood Pressure, Heart Rate	
1 Year Follow-up	Blood Pressure, Heart Rate	
2 Year Follow-up	Blood Pressure, Heart Rate	
3 Year Follow-up	Blood Pressure, Heart Rate	
4 Year Follow-up	Blood Pressure, Heart Rate	
5 Year Follow-up	Blood Pressure, Heart Rate	
6 Year Follow-up	Blood Pressure, Heart Rate	
7 Year Follow-up	Blood Pressure, Heart Rate	
8 Year Follow-up	Blood Pressure, Heart Rate	
9 Year Follow-up	Blood Pressure, Heart Rate	
10 Year Follow-up	Blood Pressure, Heart Rate	

4. Study Treatments

Subjects will be assigned to 1 of 3 possible study treatments in this study. The study treatments to be evaluated in this study are:

- OCS-01 ophthalmic suspension (QD) + Placebo (vehicle) (QD)
- OCS-01 ophthalmic suspension (BID)
- Placebo (vehicle) ophthalmic suspension (BID)

[REDACTED]
[REDACTED].

4.1 Method of Assigning Subjects to Treatment Groups

Each subject who signs an informed consent form (ICF) will be assigned a screening number. Screening numbers will be assigned in sequential order at each site beginning with 001 and will follow the two-digit site number (e.g. subject 077 at Site 99 will have Screening Number 99-077). Inclusion and exclusion criteria will be reviewed, and qualifying subjects will be enrolled into the study. The screening number will be used to identify subjects in all datasets and listings for this study.

At the Visit 2 / Day 1 visit, eligible subjects will be randomized in a [REDACTED], stratified by site, to receive either OCS-01 ophthalmic suspension (QD) + Placebo (vehicle) (QD), OCS-01 ophthalmic suspension (BID), or Placebo (vehicle) ophthalmic suspension (BID).

4.2 Masking and Unmasking

An independent biostatistician who is not otherwise involved in the study will generate the final, unmasked subject randomization as well as the final, unmasked kit list randomization. Interactive response technology will be used to provide randomization assignments.

As described in Section 4, each subject will receive [REDACTED]

[REDACTED] Dosing boxes and pouches will be labeled this way regardless of whether the product within the [REDACTED] boxes is the same [REDACTED]

5. Sample Size and Power Considerations

With a total of [REDACTED] subjects [REDACTED]

[REDACTED], the study has [REDACTED] power to detect a statistically significant treatment difference between [REDACTED]
[REDACTED]
[REDACTED]
[REDACTED]

Additionally, with this sample size, the study has █ power to detect a

6. Data Preparation

6.1 Input Data

All reported study data will be recorded on the electronic case report forms (eCRF) supplied by Statistics & Data Corporation (SDC). Only the Principal Investigator and authorized study staff according to the Delegation of Responsibilities log are entitled to make entries in the eCRF.

After data are entered into the clinical study database, electronic edit checks and data review will be performed. All data validation specifications and procedures are detailed in the Data Validation Manual as a separate document. When the database has been declared to be complete and accurate, the database will be locked. Any changes to the database after data have been locked can only be made with the approval of the Sponsor and the clinical contract research organization (if applicable), in consultation with SDC.

All analyses outlined in this document will be carried out after the following have occurred:

- All data management requirements are met according to SDC standard operating procedures, including data entry, performance of edit and validation checks, documentation and resolution of data queries, and database lock with written authorization provided by appropriate SDC and Sponsor personnel.
- Protocol deviations have been identified and status defined (major/minor deviations).
- Analysis populations have been determined.
- Randomized treatment codes have been unmasked.

6.2 Output Data

Data from remote data capture and external data will be transferred to Biostatistics and incorporated into standard formats following the Study Data Tabulation Model (SDTM). Data will then be mapped to analysis datasets using the Analysis Data Model (ADaM). Both SDTM- and ADaM-formatted data will be used to create the subject listings, while all tables and figures will be based on the ADaM-formatted data.

SDTM will follow the SDTM version 1.4 model and will be implemented using the SDTM Implementation Guide version 3.2 and the SDTM Controlled Terminology version 2016-06-24. ADaM data will follow the ADaM version 2.1 model and will be implemented using the ADaM Implementation Guide version 1.3. Both

SDTM and ADaM will be validated using Pinnacle 21 version 2.2. Any discrepancies in the validation will be noted in reviewer's guides accompanying the final data transfers.

Define.xml will be created for SDTM and ADaM using the Define-XML version 2.0 model

7. Analysis Populations

7.1 Enrolled Subjects Population

The enrolled subjects population will consist of [REDACTED]

7.2 Full Analysis Set

The full analysis set (FAS) will consist of all [REDACTED]

7.3 Per Protocol Population

The per protocol (PP) population is a [REDACTED]

7.4 Safety Population

The Safety population includes [REDACTED]

8. General Statistical Considerations

8.1 Unit of Analysis

For measurements taken at the subject level, the unit of analysis will be the individual subject and for measurements taken at the eye level, the unit of analysis will be the individual eye unless otherwise indicated. [REDACTED]

8.2 Missing or Inconclusive Data Handling

8.2.1 PARTIAL DATES

Imputation of partial or missing dates will be conducted in order to classify data as treatment-emergent or concomitant with treatment. Partial/missing start and end dates for AEs and concomitant medications will be imputed as follows:

Partial/missing start date:

- Dates with missing day only will be imputed as the 1st of the month unless the month and year are same as the month and year of first dose of study medication, in which case missing day will be imputed as the first dose day of study medication.
- Dates with both day and month missing will be imputed as 01-Jan unless the year is same as the year of first dose of study medication, in which case missing day and month will be imputed as the first dose day and month of study medication.
- Completely missing dates will be imputed as the first dose date of study medication unless the end date is on or before the first dose date of study medication, in which case missing date will be imputed as 1 Jan of the same year as the end date.

Partial/missing end date:

- Dates with missing day only will be imputed as the last day of the month unless the month and year are the same as the month and year of the last dose of study medication, in which case missing day will be imputed as the last dose day of study medication.
- Dates with both day and month missing will be imputed as 31 Dec unless the year is same as the year of the last dose of study medication, in which case missing day and month will be imputed as the last dose day and month of study medication.
- If the ongoing flag is missing or “Yes” then the date will not be imputed. If ongoing is “No” then the missing end date will be imputed as the last dose date.

The original dates will be displayed in data listings and the imputed dates will be used in derivations only (study day, treatment-emergence status, etc).

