9.3 Examination Procedures

Procedures to be performed at each study visit with regard to the study objectives are detailed in [Appendix 2: Examination Procedures, Tests, Equipment, and Techniques](#).

Visit 1 — Screening and Baseline Evaluations (-28 to -1 days prior to surgery)

- Informed consent/assent
- Demographic data
- Medical and medication history
 - Current underlying conditions, including those that began within the last 30 days, which may have been resolved before Visit 1 (Day -1 to Day -28 [prior to surgery]), must be recorded.
 - Any medications the subject is taking, as well as those the subject may have taken but discontinued within 30 days prior to Visit 1 (Day -1 to Day -28 [prior to surgery]) must be recorded.
- Urine pregnancy test (if applicable)
- Inclusion/exclusion criteria
- Ocular pain (study eye only)
- Pin-hole VA
- Slit lamp biomicroscopy

- Ocular inflammation assessment of the anterior chamber cell and flare (study eye only)
- IOP
- Dilated indirect ophthalmoscopy

Visit 2 — Day 1 (18 to 30 hours post-surgery)

- Review inclusion/exclusion criteria
- Medical and medications update
- Ocular pain (study eye only)
- Pin-hole VA
- Slit lamp biomicroscopy
- Ocular inflammation assessment of the anterior chamber cell and flare (study eye only)
- Randomization
- Dose and dispense study medication and dosing diary
- Query for AEs

Visit 3 — Day 2 (Telephone Call)

- Ocular pain (study eye only)

Visit 4 — Day 4 (\pm 1 day window)

- Medical and medications update
- Ocular pain (study eye only)
- Pin-hole VA
- Slit Lamp Biomicroscopy
- Ocular inflammation assessment of the anterior chamber cell and flare (study eye only)
- IOP
- Query for AE

Visit 5 — Day 8 (\pm 1 day window)

- Medical and medications update
- Ocular pain (study eye only)
- Pin-hole VA
- Slit lamp biomicroscopy
- Ocular inflammation assessment of the anterior chamber cell and flare (study eye only)

- IOP
- Query for AEs

Visit 6 — Day 15 (± 2 day window)

- Medical and medications update
- Ocular pain (study eye only)
- Pin-hole VA
- Slit lamp biomicroscopy
- Ocular inflammation assessment of the anterior chamber cell and flare (study eye only)
- IOP
- Query for AEs

Visit 7 — Day 22 (± 2 day window)

- Urine pregnancy test (if applicable)
- Medical and medications update
- Ocular pain (study eye only)
- Pin-hole VA
- Slit lamp biomicroscopy
- Ocular inflammation assessment of the anterior chamber cell and flare (study eye only)
- IOP

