10 ADVERSE EVENTS

10.1 Adverse Event

An AE is defined as any untoward medical occurrence associated with the use of a drug in humans, whether or not the event is considered drug-related. An AE can therefore be any unfavorable and unintended sign (e.g. an abnormal laboratory finding), symptom, or disease occurring after the subject started dosing with the study drug, without any judgment about causality. Any pre-existing medical condition that worsens after administration of the study drug will also be considered a new AE. Study drug includes the study drug under evaluation (OCS-01)

and any comparator drug, placebo (vehicle), or any other medications required by the protocol given during any stage of the study.

Documentation regarding the AE should be made as to the nature, date of onset, end date, severity, relationship to study drug, action(s) taken, seriousness, and outcome of any sign or symptom observed by the physician or reported by the subject upon indirect questioning.

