14.1 Adverse Events

An AE is defined as any untoward medical occurrence associated with the use of a drug in humans, whether or not the event is considered drug-related. Treatment-emergent adverse events (TEAE) are defined as any event that occurs or worsens on or after the day and time when first treatment is initiated.

All AEs will be coded for analysis using MedDRA, version 22.0 (or higher).

Ocular AEs are a subset of AEs and are identified as those AEs where the location field on the AE eCRF is marked as OD, OS, or OU.

Severity of an AE is defined as a qualitative assessment of the degree of intensity of an AE as determined by the Investigator or reported to him/her by the subject. The assessment of severity is made irrespective of relationship to study drug or seriousness of the event and should be evaluated according to the following scale:

- *Mild*: AE is noticeable to the subject, but is easily tolerated and does not interfere with the subject's daily activities.
- *Moderate*: AE is bothersome, possibly requiring additional therapy, and may interfere with the subject's daily activities.
- *Severe*: AE is intolerable, necessitates additional therapy or alteration of therapy, and interferes with the subject's daily activities.

The relationship of each AE to the study drug should be determined by the Investigator using these explanations:

- *Suspected*: A reasonable possibility exists that the study drug caused the AE.
- *Not Suspected*: A reasonable possibility does not exist that the study drug caused the AE.

The expectedness of an AE should be determined based upon existing safety information about the study drug using these explanations:

- *Unexpected*: an AE that is not listed in the Investigator's Brochure (IB) or is not listed at the specificity or severity that has been observed.
- *Expected*: an AE that is listed in the IB at the specificity and severity that has been observed.

An AE is classified as expected or not based on Investigator's assessment.

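### Two partial start-date rules in SAP 8.2.1 ignore the end date, so an adverse event that ended before dosing can be classed as treatment-emergent

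*SAP*

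**What the plan says.** SAP 8.2.1 imputes missing parts of adverse event (AE) and concomitant medication dates. It has three rules for start dates.

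- **Day missing.** The 1st of the month is used, unless month and year match first dose, "in which case missing day will be imputed as the first dose day of study medication".
- **Day and month missing.** 1 January is used, unless the year matches first dose, "in which case missing day and month will be imputed as the first dose day and month of study medication".
- **Completely missing.** The first dose date is used, "unless the end date is on or before the first dose date of study medication"; then 1 January of the end-date year is used.

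Only the third rule refers to the end date. The section adds that "the imputed dates will be used in derivations only", and names treatment-emergence status among those derivations. SAP 14.1 defines a treatment-emergent adverse event (TEAE) as "any event that occurs or worsens on or after the day and time when first treatment is initiated", with no condition on the end date.

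On collection, Protocol 10.1 describes an AE as "occurring after the subject started dosing with the study drug". In Protocol 9.3 the first AE query is at Visit 2, listed after the step "Dose and dispense study medication and dosing diary".

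**The concern.** The third rule shows that the authors meant a known pre-dose end date to override the default of first dose. The two partial-date rules omit that override. As a result, a record with some start information can be classed as treatment-emergent when the same record with none is not. The imputed start can also fall after the recorded end, which is impossible.

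At stake are the TEAE tables: an event known to have finished before the first drop could be counted against the study arm. The same rules govern concomitant medications, but the definitions of prior and concomitant use in SAP 11.2 are redacted, so no effect there can be confirmed.

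**Working it through.** The plan gives no figure to reproduce. The check applies the three rules as written to one record, then repeats it with an end-date condition added to the two partial-date rules.

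**Inputs.** The rules are from SAP 8.2.1. The TEAE test is from SAP 14.1, applied by date: TEAE if imputed start ≥ first dose date. SAP 14.1 also mentions time, but SAP 8.2.1 imputes none, so a start placed on the first dose day is read as treatment-emergent. The example dates are assumptions: first dose 20-Oct-2019, recorded end 12-Oct-2019.

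| Recorded start | Start as written | TEAE? | Start with end-date check | TEAE? |
|---|---|---|---|---|
| Oct-2019 | 20-Oct-2019 | yes | 01-Oct-2019 | no |
| 2019 | 20-Oct-2019 | yes | 01-Jan-2019 | no |
| none | 01-Jan-2019 | no | 01-Jan-2019 | no |

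As written, 2 of the 3 rules class the record as treatment-emergent; with the check, 0 of 3 do. In the first two rows the start as written is 20 − 12 = 8 days after the recorded end.

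**Boundary and partial end dates (same first dose).**

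- End on 20-Oct-2019: both partial-date rules give 20-Oct-2019 with or without the check. The completely-missing rule gives 01-Jan-2019.
- Start 2019, end Sep-2019: the latest possible end is 30-Sep-2019, before first dose. As written the start is 20-Oct-2019; with the check it is 01-Jan-2019.
- End Oct-2019 or 2019: unchanged at 20-Oct-2019, because the event may have run past first dose.

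**Behaviour over many dates.** All start and end pairs in the 29 days before first dose were enumerated for 365 assumed first-dose dates: (29 × 30 / 2) × 365 = 435 × 365 = 158,775 pairs, all ending before dosing.

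- Day missing, as written: 56,522 / 158,775 = 35.6% become TEAEs.
- Day and month missing, as written: 150,220 / 158,775 = 94.6%.
- Completely missing, as written: 0.
- All three rules with the check: 0.

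These percentages weight every pair equally. They show how the rules behave and do not estimate how often the problem would occur in this trial.

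**Effect of one record.** Protocol 6.1 gives about 150 subjects. The allocation is redacted; an equal split is assumed, so 150 / 3 = 50 per arm. One affected subject adds at most 1/50 = 2.0 percentage points to a TEAE row. For arms of 75 and 30 the figures are 1/75 = 1.3 and 1/30 = 3.3 points.

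**The case against.** The strongest reply is that such records should hardly exist. Protocol 10.1 places AEs after the start of dosing. Protocol 9.3 gives pre-dose events another home: medical history at Visit 1, and a medical update at Visit 2 listed ahead of dosing. The record must also be entered as an AE anyway, have a partial start that matches first dose, have an end known to precede dosing, and survive the edit checks and query resolution required by SAP 6.1. Original dates remain visible in the listings, and any error is in the cautious direction for safety.

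This stands as a limit on frequency and impact. It does not remove the defect. AEs are monitored throughout the study (Protocol 9.3), so stray records are possible. SAP 14.1 lists all AEs and flags the TEAEs among them, so the plan allows for AE records that are not treatment-emergent, and its own third rule handles ends on or before first dose. No visible text supplies the missing check for the other two rules.

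A second objection is that the proposed check uses an end before first dose, while the third rule uses an end on or before it. An event ending on the dosing day is then still classed differently according to how much of its start is known. That is true. It is a deliberate choice: an event ending that day may have followed the dose, so keeping it is conservative.

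**Conclusion.** The concern holds. Where the known part of the start date matches first dose and the recorded end precedes it, SAP 8.2.1 produces a start later than the end and makes the event treatment-emergent by date. That is an error in a stated rule, not a lack of detail.

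The consequence is minor. The documents give no count of affected records, and it should be small. The error can only over-count TEAEs and has no bearing on efficacy. The per-subject effect of at most 2.0 points (1.3 to 3.3 for arms of 75 down to 30) rests on assumed arm sizes. The TEAE classification rests on comparing dates, since no time is imputed. Confidence is high about the rule itself; nothing in the documents shows that the trial's tables would change materially.

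**What to change.** Add to both partial start-date rules in SAP 8.2.1:

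> If the recorded end date (or the latest date a partial recorded end date allows) is before the first dose date, the start is imputed as the 1st of the known month, or 01-Jan of the known year. Records ending on the first dose date stay treatment-emergent under these two rules.

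Use the recorded end date, not an imputed one, so that one imputation does not drive another. State why the boundary differs from the rule for completely missing dates: an event ending on the dosing day may have followed the dose.

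The cost is two sentences and a small derivation change. The one risk is that a wrongly recorded end date would make a genuine event non-emergent, so affected records should be queried before database lock; SAP 6.1 already requires query resolution by then. Worsening after dosing is not lost, because Protocol 10.1 states: "Any pre-existing medical condition that worsens after administration of the study drug will also be considered a new AE".
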